12.2. Reporting Procedures

Adverse Event Term

An adverse event term must be provided for each adverse event. Wherever possible a valid term listed in the Common Terminology Criteria for Adverse Events (CTCAE) v5.0 should be used. This is available online at:

http://evs.nci.nih.gov/ftp1/CTCAE/

Severity grade

Severity grade of each adverse event must be determined by using CTCAE v5.0. This is available online at:

http://evs.nci.nih.gov/ftp1/CTCAE/

Causality

The relationship between the treatment and an adverse event will be assessed.

For AEs, the local PI or designee will assess whether the event is causally related to trial treatment.

For SAEs, a review will also be carried out by the Sponsor's delegate.

Causal relationship to each trial treatment must be determined as follows:

- Related (reasonable possibility) to a trial treatment
- Not related (no reasonable possibility) to a trial treatment

UCL CTC will consider events evaluated as related to be adverse reactions.

Responsibility for reporting safety events following transfer of care

In the event of transfer between trial sites

UCL CTC must be informed if a patient's care is transferred to another trial site (see section 15.4 – Transfer of Care). The trial site caring for the patient at the time of awareness of AE, SAE, AESI, Urgent Event onset or pregnancy is responsible for completing and sending relevant reports to UCL CTC. When the patient's care is transferred, the referring site must provide sufficient information about the patient's trial participation (i.e. a copy of the patient's completed CRFs up to the date of transfer) to the new site to allow them to complete SAE reports.

In the event of transfer between a trial site and a non-trial site

The trial site will remain responsible for completing and sending AE, SAE, AESI Urgent Event and pregnancy reports to UCL CTC. If a patient is discharged to the care of a non-trial site, the Pl/study team at the trial site should ensure that they are sent regular updates on the patient's progress and notified of any admissions or significant medical developments (including relapses and deaths), in order that the site's reporting responsibilities can be fulfilled.

12.2.1. Reporting of Adverse Events (AEs)

All adverse events that occur between the start of nivolumab treatment and 3 months post last nivolumab administration or commencement of next treatment for lymphoma (whichever is earlier) must be recorded in the the trial CRFs.

The reporting period has been selected as the patients are followed up at 1, 2, 3 months, then moving to 3 monthly follow up schedule. It is anticipated that most patients will have proceeded to further lymphoma treatment by the 3 month timepoint.

Adverse events meeting the definition of a Serious Adverse Event (SAE) or Adverse Event of Special Interest (AESI) must also be reported to UCL CTC using the trial specific SAE Report. Also refer to section 12.2.2 (Reporting of Serious Adverse Events (SAEs)) and section 12.4 (Adverse Events of Special Interest). Adverse events meeting the definition of an Urgent Event must also be reported on an Urgent Event form (also refer to section 12.5 Urgent Events).

Pre-existing conditions do not qualify as adverse events unless they worsen.

12.2.2. Reporting of Serious Adverse Events (SAEs)

All SAEs that occur between the start of nivolumab treatment and 5 months post last nivolumab administration or commencement of next treatment for lymphoma (whichever is earlier), including

stem cell transplant (or after this date if the site investigator feels the event is related to nivolumab) must be submitted to UCL CTC.

The reporting timeframe takes into account the potential risk of delayed reactions from nivolumab (5 times half life, approximately 5 months), but is balanced against the fact that patients are expected to proceed to further lymphoma treatment after nivolumab, which will have a similar (or worse) toxicity profile compared to nivolumab. The different reporting requirements for AESIs (see section 12.4 below) allows for continued reporting of important nivolumab-specific reactions (such as immune-related events), even after the start of a new lymphoma treatment.

SAEs must be reported by fax or email within **24 hours** of observing or learning of the event, using the trial specific SAE Report. All sections on the SAE Report must be completed. If the event is **not being reported within 24 hours** to UCL CTC, the circumstances that led to this must be detailed in the SAE Report to avoid unnecessary queries.

The following AESIs must be reported on the SAE report form:

- Autoimmune diarrhoea / colitis
- Autoimmune pneumonitis
- Autoimmune hepatitis
- Autoimmune dermatitis
- Immune related endocrinopathies
- Autoimmune renal toxicity
- Autoimmune neurological toxicity
- Autoimmune uveitis
- Potential drug induced liver injury (pDILI)
- Overdoses (regardless of whether the patient experiences any adverse events as a result)
- Grade 3 or 4 infusion reactions to nivolumab

See section 12.4 for further information.

To summarise, the SAE reporting requirements for non-autoummune events, based subsequent treatment, are as follows (see section 12.4 for details of reporting windows for autoimmune events):

Next Planned Treatment	Reporting window for non-autoimmune SAEs
No treatment	From first administration of nivoumab until 5 months post last dose of trial treatment.
	(N.B. if the patient relapses and starts new treatment within 5 months after completing nivolumab, SAEs will no longer be collected).
Further chemotherapy	From first administration of nivoumab until 5 months post last dose of trial treatment or first administration of next line of chemotherapy, whichever is sooner.
Autologous stem cell transplant	From first administration of nivoumab until 5 months post last dose of trial treatment or first administration of pre-transplant chemotherapy, whichever is sooner.
Allogeneic stem cell transplant	From first administration of nivoumab until 5 months post last dose of trial treatment or commencement of transplant conditioning, whichever is sooner.

Exemptions from SAE Report submission

For this trial, the following events are exempt from requiring submission on an SAE Report, but must be recorded in the relevant sections of the trial CRFs:

- Events that occur more than 5 months post last trial treatment administration unless:
 - o considered to be a late effect of the trial treatment
 - o it is a pregnancy related event (see section 12.8)
- Events that occur after the commencement of further treatment for lymphoma unless:
 - An autoimmune event classed as an AESI (see section 12.4)
- Disease progression (including disease related deaths, unless considered related to the trial treatment). N.B. disease progression and deaths from any cause are Urgent Events – see section 12.5)
- The following post-allogeneic transplant toxicities, which should be reported as urgent events (see section 12.5):
 - Grade 3/4 graft-vs-host disease (patients who have allogeneic transplant only)
 - Hyperacute graft-vs-host disease (patients who have allogeneic transplant only)
 - o non-infectious febrile episodes requiring steroid therapy (including steroid-responsive febrile syndrome; patients who have allogeneic transplant only)
 - Sinusoidal obstruction syndrome/ veno-occlusive disease (patients who have allogeneic transplant only)

Please note that hospitalisation for elective treatment (including further treatment for lymphoma), palliative care, for logistical or socio-economic reasons does not qualify as an SAE.

Completed SAE Reports must be faxed or emailed to UCL CTC within 24 hours of becoming aware of the event

[figure not shown]
[contact] Email: [contact]

SAE Follow-Up Reports

All SAEs will be followed up until resolution and until there are no further queries.

Sites must ensure any new and relevant information is provided promptly. If the event term changes or a new event is added, the causality must be re-assessed by an Investigator. If the event is not being reported within 24 hours to UCL CTC, the circumstances that led to this must be detailed in the SAE/SAR Report to avoid unnecessary queries.

Adverse Event Reporting Flowchart

SAE Processing at UCL CTC

On receipt of the SAE Report, UCL CTC will check for legibility, completeness, accuracy and consistency. Expectedness will be evaluated, to determine whether or not the case qualifies for expedited reporting, using the RSI (the approved Investigator Brochure (IB) for Nivolumab).

The CI, or their delegate (e.g. a clinical member of the TMG), may be contacted to review the SAE and to perform an evaluation of causality on behalf of UCL CTC. If UCL CTC has considered expectedness difficult to determine, the CI, or their delegate, will be consulted for their opinion at this time.

UCL CTC will submit all SAE Reports concerning patients who have received Nivolumab to BMS according to the timelines outlined in the agreement between UCL and BMS.

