18.2.2. Analysis of secondary endpoints and secondary analyses

Survival endpoints:

Progression free survival (PFS)

PFS time will be measured from the date of the PET scan after first or second line salvage treatment (PET0) until the date of progression or death (whichever comes first). Patients who are alive and progression free will be censored at the date last seen.

Overall survival (OS)

OS time will be measured from the date of the PET scan after first or second line salvage treatment (PET0) until the date of death. Patients who are alive will be censored at the date last seen.

Analysis of PFS and OS will take place once we have 1 year follow-up for all patients. Kaplan Meier survival analyses will be used for both.

Subgroup analyses will be performed for responders and non-responders i.e. do patients with a PMR do worse than those with a CMR after nivolumab treatment. Kaplan Meier survival analysis and Cox regression may be used, although this will be dependent on the numbers of patients with a response and the numbers of events.

PFS and OS will also be analysed by further treatment i.e. did the patient go on to have an allograft or autograft, though we acknowledge that numbers will be very small so analyses will be descriptive.

CMR/PMR rates

Proportions of patients achieving CMR and PMR will also be presented.

Adverse events:

Analysis will focus on grade 3/4 adverse events. The worst grade seen per patient will be shown for each event type.

AESIs will be reported in more detail, with autoimmune events of any grade presented. All analysis will be descriptive.

Transplant related mortality and the rate of serious complications of allo SCT will presented, though again, it is likely only descriptive statistics will be used.

Other analyses:

The association between pre-nivolumab biological parameters and response to nivolumab will be investigated. As numbers will be very small mostly descriptive statistics will be used i.e. numbers and percentages will be presented for binary/categorical data and means and medians (with ranges) for continuous measurements.

We will also look at changes in TARC levels in responders and non-responders.

PET negative patients not treated with nivolumab

We will look at PFS, OS and subsequent treatments for patients who are PET negative following first or second line salvage treatment (i.e. at PET0).

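### Sections 12.2.1 and 12.2.2 give sites different rules for recording serious events once the next lymphoma treatment starts, so some of those events may reach the nivolumab toxicity summary

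*Protocol*

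**What the plan says.** Four parts of the protocol bear on this.

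- **Section 12.2.1** requires all adverse events to be recorded from the start of nivolumab until "3 months post last nivolumab administration or commencement of next treatment for lymphoma (whichever is earlier) must be recorded in the the trial CRFs". It adds: "It is anticipated that most patients will have proceeded to further lymphoma treatment by the 3 month timepoint".
- **Section 12.2.2, opening and table,** runs serious event collection to 5 months after the last dose or next lymphoma treatment, whichever is earlier. The opening adds later events that the investigator considers related to nivolumab. For a patient with no planned treatment who relapses, the table says that if the patient "starts new treatment within 5 months after completing nivolumab, SAEs will no longer be collected".
- **Section 12.2.2, exemption list,** begins: "the following events are exempt from requiring submission on an SAE Report, but must be recorded in the relevant sections of the trial CRFs". Two of its entries are "Events that occur more than 5 months post last trial treatment administration unless" (the exceptions being late effects of trial treatment and pregnancy-related events) and "Events that occur after the commencement of further treatment for lymphoma unless" (the only exception being an autoimmune event classed as an adverse event of special interest).
- **Section 18.2.2** describes the safety analysis: "Analysis will focus on grade 3/4 adverse events. The worst grade seen per patient will be shown for each event type". It presents transplant-related mortality and serious complications of allogeneic transplant separately.

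**The concern.** Safety and toxicity of nivolumab is a named secondary endpoint (section 3.2) in a trial with no control arm, so what counts as nivolumab toxicity depends heavily on when recording stops. Most patients are expected to have started further lymphoma treatment by month 3, and 12.2.2 itself expects that treatment to be at least as toxic as nivolumab. If one site stops recording at that point and another keeps entering serious events because the exemption list tells it to, the two sites contribute data collected under different rules. A summary of each patient's worst grade would then mix nivolumab toxicity with that of chemotherapy or transplant, with no comparator to separate them. In the other direction, a site that follows the exemption list literally could fail to send SAE Reports that other sections require.

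**Working it through.** No figure in the protocol is in dispute, so the check is to put the same events through each rule.

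| Event | 12.2.1 | 12.2.2 opening and table | 12.2.2 exemption list | Other text |
|---|---|---|---|---|
| A. Serious infection, unrelated to nivolumab, after transplant conditioning begins, between the day 30 and day 60 visits | Outside window | Not collected | No SAE Report, but CRF recording required | 9.6.2: adverse event assessment due at day 60, no stop stated for new treatment |
| B. Serious unrelated event more than 5 months after last dose, no further treatment | Outside window | Not collected | No SAE Report, but CRF recording required | 9.6.2: from month 6, only late nivolumab toxicity is assessed |
| C. Serious non-autoimmune event judged related to nivolumab, after further treatment | Outside window | Must be submitted | Exempt, because only autoimmune events of special interest are kept | None |
| D. Potential drug-induced liver injury after further treatment, within 5 months of last dose | Outside window | On the list of events for the SAE form | Exempt if read literally: 12.1 lists it separately from the autoimmune events | 12.4.2: SAE report to 5 months, no stop at new treatment |

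In A and B, two rules say the event is not collected and a third says it must be recorded. In C and D, one rule requires an SAE Report and another waives it. The exemption list is the odd one out each time.

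**From recording to analysis.** Section 18.2.2 takes the worst grade per patient for each event type. As written in the protocol it states neither an onset window nor a relatedness limit. An event like A, if entered on the adverse event pages, could therefore be tabulated.

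**Can the size be derived?** Let b be the share of patients with a grade 3/4 event from nivolumab, s the share going on to transplant, and t the share of those with a grade 3/4 event recorded afterwards. Assuming independence, the share with any such event is b + (1 − b) × s × t. The background in section 2.1 gives 16–22% as the grade 3 rate, used here for b. The protocol gives neither s nor t, so these are assumptions.

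- t = 0: 16% to 22%, that is 4.8 to 6.6 of 30 patients.
- b = 0.16, s = 0.5, t = 0.25: 0.16 + 0.84 × 0.125 = 0.265, about 8 of 30.
- b = 0.22, s = 0.9, t = 1: 0.22 + 0.78 × 0.9 = 0.922, about 28 of 30.

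The range runs from no effect to nearly every patient, entirely according to the assumed s and t. It also concerns any event per patient, whereas 18.2.2 reports by event type. It is not an estimate of contamination; it shows that the document does not fix one.

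**The case against.** The case that this is only loose wording is fair in several respects.

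- The exemption list concerns events that would otherwise need an SAE Report. The conflict is about serious events, not all adverse events, and elective admission for further lymphoma treatment is stated not to count as serious.
- The CRF sections in question are not defined. Progression, death and the named post-allogeneic events have their own forms, and late toxicity has its own assessment, so the clause need not point to the adverse event pages. The reporting flowchart in 12.2.2 could not be read in the copy used here and may show the routing.
- Sections 12.2.1 and the 12.2.2 table both show an intention to stop at next treatment, and no general adverse event assessment is scheduled after month 3.
- Section 12.2.1 says what must be recorded; it does not expressly forbid recording more.
- An analysis window is commonly set in the SAP, which was not available.

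These points limit the finding but do not remove it. An SAP can filter by onset date, but it does not correct contradictory instructions to sites, nor restore an SAE Report that was never sent. The undefined CRF sections are part of the problem. And before month 3 the 9.6.2 assessments continue with no stated stop at new treatment, when most patients are expected to have started it.

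Two stronger readings are tempting. A reader might infer that the summary will mostly describe transplant toxicity. The documents do not support that: named allogeneic complications are collected and presented separately, entry of other events is possible but not certain, and any large figure needs an assumed event rate among transplanted patients. A reader might also infer that fatal events have no place in the analysis. Section 18.2.2 only sets a focus on grade 3/4, its worst-grade rule does not exclude grade 5, and all deaths go on their own form.

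**Conclusion.** The concern holds in a limited form. The protocol contains conflicting rules for serious events after the next lymphoma treatment or more than 5 months after the last dose. For nivolumab-related serious events and potential drug-induced liver injury after further treatment, it both requires and waives the SAE Report. Sites can follow different rules in good faith, and some serious events from chemotherapy, autologous transplant or other allogeneic toxicity may enter the nivolumab worst-grade summary. The size cannot be derived from the document. Whether those events reach the summary depends on which CRF pages sites use and on any onset filter in the SAP, neither of which is known here. The primary endpoint and its decision rule are unaffected. It should be corrected because it concerns a secondary endpoint and safety reporting, and the correction is cheap.

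**What to change.** 1. In the 12.2.2 exemption list, replace the general recording clause with one that agrees with 12.2.1, the opening and table of 12.2.2, and 12.4.2. Name the later events that are still recorded or reported: adverse events of special interest, including potential drug-induced liver injury; urgent events; and events judged related to nivolumab. State the form or CRF section for each.
2. Widen the exception for events after further lymphoma treatment so that it no longer keeps only autoimmune events.
3. In 9.6.2, say whether the adverse event assessments at months 1 to 3 continue once new lymphoma treatment has begun, and for which events.
4. In 18.2.2, base the adverse event summary on events with onset inside the 12.2.1 window and show later events in a separate listing.

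The cost is a protocol wording change, matched in the SAP and CRF guidance, with no new data. The only loss is that later unrelated events move from the summary to a listing.

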8.5.1.8 Management of other immune-related adverse reactions

Adequate evaluation should be performed to confirm aetiology and exclude other causes.

See summary of product characteristics for detailed guidance on management of individual toxicities.

CTCAE v5 grade	Action – trial treatment	Recommended management of toxicity
Grade 1	Continue nivolumab treatment at 240mg.	Treatment for symptoms as per local policy.
Grade 2 (first occurrence)	Delay nivolumab treatment Restart nivolumab at 240mg if/when returns to ≤G1. If steroids given, patient must have been weaned to ≤10mg per day (or equivalent) before restarting treatment. Maximum permitted delay 4 weeks.	Treat symptoms as per local guidelines. Steroid treatment as per local policy; taper prior to restarting nivolumab.
Grade 3 (first occurrence – except myocarditis – see below)	Delay nivolumab treatment. Restart nivolumab at 240mg if/when returns to ≤G1. If steroids given, patient must have been weaned to ≤10mg per	Treat symptoms as per local guidelines. Steroid treatment as per local policy; taper prior to restarting nivolumab.

	day (or equivalent) before restarting treatment.	
	Maximum permitted delay 4 weeks.	
Grade 3 myocarditis	Permanently discontinue nivolumab treatment.	Refer for specialist opinion. Manage as per local policy.
Grade 4 or recurrent grade 3;	Permanently discontinue	Treat symptoms as per local
Persistent grade 2 or 3 despite	nivolumab treatment.	guidelines.
intervention;		Steroid treatment as per local
Inability to reduce corticosteroid		policy.
dose to 10mg prednisolone per day or equivalent		Seek specialist opinion.

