12.4.2 Potential Drug Induced Liver Injury (pDILI)

All occurrences of potential DILIs, meeting the defined criteria below, must be reported as SAEs.

Potential drug induced liver injuries should be reported from the first administration of nivolumab until five months post-treatment (or after this date if the investigator feels the event is related to nivolumab).

Event	Description	Form required	Timeframe
Potential drug induced liver injury (pDILI)	AST or ALT >3 x ULN and Total bilirubin >2 x ULN, without initial findings of cholestasis (elevated serum alkaline phosphatase)	SAE report	Within 24 hours of diagnosis
	and No other immediately apparent causes of transaminase elevation and hyperbilirubinemia, including, but not limited to, viral hepatitis, pre-existing chronic or acute liver disease, or the administration of other drug(s) known to be hepatotoxic.		

Cases of pDILI must be reported on the trial-specific SAE report by fax or email: [contact]

Email: [contact]

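### Section 12.2.2 gives opposite instructions on nivolumab-related SAEs once further lymphoma treatment has started

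*Protocol*

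**What the plan says.** **Main rule (12.2.2).** The routine duty covers "All SAEs that occur between the start of nivolumab treatment and 5 months post last nivolumab administration or commencement of next treatment for lymphoma", whichever comes first, with stem cell transplant counted as next treatment. The sentence then extends the duty: "or after this date if the site investigator feels the event is related to nivolumab) must be submitted to UCL CTC". The rationale that follows ties 5 months to delayed reactions (five half-lives), weighs this against the toxicity of the next treatment, and relies on the AESI rules to keep immune-related reactions reportable afterwards.

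**Summary table (12.2.2, non-autoimmune SAEs).** Every row closes at 5 months or at the next treatment, and none has a relatedness exception. The row for patients with no planned treatment notes that "if the patient relapses and starts new treatment within 5 months after completing nivolumab, SAEs will no longer be collected".

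**Exemption list (12.2.2).** Three bullets matter here:
- Events beyond 5 months are exempt, except late effects of trial treatment and pregnancy-related events.
- The second bullet reads "Events that occur after the commencement of further treatment for lymphoma unless", and its single exception is "An autoimmune event classed as an AESI (see section 12.4".
- Progression and disease-related deaths are exempt, except where related to trial treatment.

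Exempt events must still be entered in the CRFs.

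**pDILI (12.4.2).** "Potential drug induced liver injuries should be reported from the first administration of nivolumab until five months post-treatment", and later if thought related. Next treatment is not given as a cut-off. Section 12.1 lists pDILI among the AESIs, as an item separate from the autoimmune ones.

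**Timing (12.2.1).** "It is anticipated that most patients will have proceeded to further lymphoma treatment by the 3 month timepoint".

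**The concern.** A site with a serious event that its investigator attributes to nivolumab, in a patient who has already started chemotherapy or conditioning, cannot follow all of section 12.2.2. The main rule says submit. The exemption list says no SAE Report is needed, and the table puts the event outside the window. The exemption list and the table are the parts a busy site is likely to consult.

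This is a bridge-to-transplant trial with nivolumab safety as a secondary endpoint, so the time after the next treatment starts is not marginal. If sites follow the exemption, related serious events in that period would not reach the sponsor by the expedited route.

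**Working it through.** There is no plan figure to reproduce. The check sets the rules side by side.

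**Step 1: what the cut-off date in the main rule refers to.** The relatedness clause directly follows the two end-points and the mention of transplant. Its natural antecedent is therefore the earlier of the two, which includes the start of next treatment. Reading it as the 5-month date alone would soften the conflict but not remove it (event B below).

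**Step 2: test events, all after the next lymphoma treatment has started.**

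| Event | Main rule or specific AESI rule | Second exemption bullet | Consistent? |
|---|---|---|---|
| A. Serious, judged related, not an AESI, within 5 months of last dose | Submit (12.2.2) | Exempt | No |
| B. As A, but beyond 5 months | Submit (12.2.2); the first exemption bullet also keeps it reportable as a late effect | Exempt | No |
| C. pDILI not classed as autoimmune hepatitis, within 5 months | Report (12.4.2) | Exempt | No |
| D. Listed autoimmune AESI, within 5 months | Report (12.4.1, which says so explicitly) | Not exempt | Yes |
| E. Serious, unrelated, not an AESI | Not required | Exempt | Yes |

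The summary table sides with the exemption for A and B. The neighbouring bullets, on late events and on disease-related deaths, both keep a relatedness exception. Only the second bullet lacks one.

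**Step 3: what depends on the SAE Report.** Under the SAE processing text of 12.2.2, UCL CTC evaluates expectedness when the report arrives. Section 12.3 starts from that evaluation, and the report is also what is forwarded to the drug supplier. With no report, none of these steps starts.

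**Step 4: what is still recorded.** Exempt events must go in the CRFs, but the AE window in 12.2.1 closes at the earlier of 3 months or next treatment. Late nivolumab toxicity is assessed at months 6, 9 and 12 and annually (9.6.2), and annually after progression (9.8). Follow-up CRFs are due within 4 weeks of the visit, against 24 hours for SAE forms (11.3).

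**Step 5: how much of the window is affected.** Inputs: a 5-month delayed-reaction window (12.2.2), and next treatment expected in most patients by 3 months (12.2.1). For a patient who starts at month 3:

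(5 − 3) / 5 = 2/5 = 40% of the window.

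An earlier start gives a larger share, so for these patients 40% is a minimum.

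**The case against.** **Stopping at next treatment is deliberate and explained.** This stands for unrelated events: the next treatment's toxicity would swamp the signal. It does not explain excusing events the investigator attributes to nivolumab, which the sentence just before that rationale requires.

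**Events are not lost.** A reader might infer that related serious events disappear from the safety endpoint. The documents do not support that. CRF recording and late-toxicity visits remain (step 4). Deaths from any cause are Urgent Events due within 24 hours (12.5.3). Severe or hyperacute GVHD, steroid-treated non-infectious fever and veno-occlusive disease are Urgent Events up to day 100 after an allograft (12.5.1). The adverse event analysis in 18.2.2 is not stated to rest on SAE Reports alone. The loss is in expedited reporting.

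**The pDILI gap is narrow.** Most pDILI cases would also fit the broad autoimmune hepatitis description in 12.4.1, which stays reportable. This largely stands. But 8.5.3 asks sites to find out whether a case is pDILI or autoimmune liver disease, so the protocol treats them as different diagnoses, and a case settled as pDILI falls into the conflict.

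**Myocarditis.** A reader might infer that a related "Grade 3 myocarditis" after conditioning is plainly exempt, because section 8.5.1.8 names it and the AESI lists in 12.1, 12.2.2 and 12.4.1 do not. That is too strong. Section 8.5.1, under which 8.5.1.8 sits, says autoimmune toxicities are AESIs needing expedited reporting. The status is ambiguous, and the lists need aligning.

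**Conclusion.** The contradiction is real and is wrong as written. For a related, non-AESI serious event after next treatment, the main rule of 12.2.2 cannot be squared with the second exemption bullet and the summary table. For pDILI, the same bullet conflicts with 12.4.2. The consequence is a possible missing SAE Report, and with it the expectedness and SUSAR assessment, during at least about 2 of the 5 months of the protocol's own delayed-reaction window for the majority expected to move on by 3 months.

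This rests on the natural reading of the main rule's cut-off and on the protocol's own expectation about timing. The 40% is a share of time, not of events. A reader might go further and take the share up to 80% by supposing a start at 1 month, or turn it into a missed rate such as 1 in 30 treated patients (3.3%) falling to 0%. The protocol gives neither a 1-month start nor a rate of late related SAEs, and a fall to 0% would need the event to vanish from the CRFs as well.

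**What to change.** 1. In the exemption list of 12.2.2, replace the second bullet's single exception with: *unless judged related to nivolumab, or an AESI inside its section 12.4 reporting window (pDILI included)*.
2. Qualify each row of the 12.2.2 summary table, and the note in its first row, in the same way.
3. Reconcile the AESI lists in 12.1, 12.2.2 and 12.4.1 with section 8.5.1, so that it is explicit whether the class in 8.5.1.8 is reportable as an AESI.

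The cost is an amendment to reporting wording, matching guidance on the SAE form, and a few more SAE reports. No treatment rule changes.
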